5.7.4. Loop-mediated isothermal amplification (LAMP)
5.8. Statistical Analysis Plan20
5.9. Data analysis and interpretation
5.10. Benefits and beneficiaries of the proposed study22
5.11. Dissemination of findings
5.12. Ethical Considerations
6.0. WORK PLAN
7.0 English Version of Questionnaire2
8.0 References

SUMMARY

Background: Malaria is one of the major public health problems in sub-Saharan Africa. It contributes significantly to maternal and fetal morbidity and mortality in affected countries.

Objective: The aim of this study is to evaluate the impact of enhanced case detection using molecular testing (LAMP) on maternal and infant morbidity and mortality in a prospective study design.

Method: A pragmatic randomized control diagnostic trial will be conducted from October 2020 until October 2021 in pregnant mothers at sites in Ethiopia. Both symptomatic and asymptomatic first and early second trimester pregnant women will be included in the study and individually randomized to either standard of care or enhanced cased detection arms using LAMP for malaria. Women (n=2583) will be enrolled during a twelve-months period encompassing the peak transmission seasons and then followed until delivery. In the standard of care arm, venous blood sample will be collected from each study participant and the presence of *Plasmodium* infection will be diagnosed by microscopy in symptomatic patients. Pregnant women who test positive for malaria will be referred and treated for malaria with quinine or artemisinin combination therapies (ACTs) as per national guidelines. In the intervention arm, mothers who are symptomatic or asymptomatic will be tested by a commercially available CE-approved LAMP malaria test and microscopy/RDT for malaria at each clinic visit and treated if positive by any test. Pregnant mothers who require treatment will be referred and treated with either quinine or artemisinin combination therapy (ACTs) as per national guidelines. The primary outcome is the proportion of deliveries with low birth weight based on WHO definition, with secondary outcomes of:(i)absolute birth weight; (ii) maternal hemoglobin;(ii) neonatal hemoglobin at birth;(iv) neonatal mortality; (v) stillbirth; and (vi) prematurity in each arm of the study.

Result Dissemination plan: The results of this study will be presented at national and international scientific conferences. It will also be published in a reputable journal.

Work plan and budget: This study will be conducted from October 2020 to October 2021. The study is funded by Grand Challenges Canada, FIND, AHRI, University of Calgary, with support from test manufacturers (Human Diagnostics, Wiesbaden, Germany and Meridien Diagnostics, Cincinatti, USA)

Key words: Malaria, LAMP, Pregnancy

1. INTRODUCTION

1.1. Background

In 2017 about 219 million cases of malaria occurred worldwide and approximately 435,000 people died of the disease globally according to the World Health Organization. The sub-Saharan region experienced around 92% of these deaths [1]. Mortality is concentrated around several high-risk groups, including pregnant women and infants. In Africa, 30 million women living in malaria-endemic areas become pregnant each year. Up to 200,000 newborn deaths each year result from malaria in pregnancy. Malaria infection has an adverse impact on pregnancy in endemic countries. Diagnosis of malaria in pregnancy is limited by microscopy and RDT both with poor sensitivity. Malaria, particularly due to *P. falciparum*, in pregnant women increases the risk of maternal death, miscarriage, stillbirth and neonatal death. In areas of seasonal malaria transmission, pregnant counterparts. The World Health Organization (WHO) recommends prompt diagnosis and appropriate treatment of malaria. However, diagnostics are lacking in detecting low-level infections typically found in pregnant women because malaria parasites are sequestered in the placenta and not present in the peripheral blood in large quantities.

It is well documented that sequestration in the placenta leads to adverse outcome for the mother and infant especially related to anemia and birth weight [2,3]. Both anemia and low birth weight are predictors of poor outcomes in infancy for the child. Malaria in pregnancy therefore affects not only the current generation but the next, hobbling cognitive development and thus economic productivity. In other parts of sub-Saharan Africa, the issue is so profound mothers are exposed to antimalarials during pregnancy without testing to prevent malaria. But this comes at a cost since empiric use of anti-malarial drugs contributes to resistance and may lead to side effects.

The National Strategy to eliminate malaria in Ethiopia and other sub-Saharan countries in the next 10 years will demand highly sensitive diagnostics in patients with such low-level infections. Our group has validated a DNA based test for malaria called "LAMP" and shown up to 30% greater detection of malaria in pregnant women who are symptomatic and even greater than 90% detection when screening "asymptomatic" women. We are now actively seeking to scale up this heath care

technology to determine the true impact across Ethiopia with key partners. Meaningful impact will be measured by determining health outcomes for mother and child, especially reduction in infant anemia and improvement of birth weight.

1.2. Literature Review

There are many different types of tests available for malaria. Microscopy of stained blood smear and rapid diagnostic techniques (RDTs) are the most widely used laboratory methods. Molecular tests for malaria such as polymerase chain reaction (PCR) are highly sensitive but not feasible in resource-limited settings due to high capital equipment costs, laboratory infrastructure needs, reagent supply chain, and specialized training. The process of the PCR is also time-consuming resulting in delays in reporting the results to clinicians which, in turn, compromises timely management of patients. Traditionally, laboratory diagnosis has relied on the identification of parasites in a peripheral blood film using either Giemsa, Wright, or Field stain[4,5]. Microscopy is an accurate tool but requires well-trained laboratory technicians. In experienced hands, the limit of detection is about 50 parasites/µL[5]. Rapid diagnostic tests (RDTs) are alternatively used for the diagnosis of malaria in all health facilities or through rural health extension and outreach. RDTs are easier to perform and used for screening of malaria in remote areas where electricity and other resources are limited [6,7]. However, microscopy and RDTs cannot reliably detect lower-density parasitemia (<100 parasites/ μ L)[5]. As most adverse outcomes caused by malaria are because of wrong, late, or unavailable diagnosis, there is a need to find a new alternative diagnostic tool for field diagnosis of malarial infection [8].

Loop-mediated isothermal amplification (LAMP) is a potential point of care test (POCT) that provides an alternative to microscopy and RDTs [9–11]. It is a molecular method, which in comparison to PCR is cheaper, simpler, and faster, overcoming three major disadvantages of PCR. The LAMP test is a nucleic acid amplification method that relies on a strand-displacement DNA polymerase which also retains reverse transcriptase activity. The principal merit of this method is that no denaturation of the DNA template is required, and thus, the LAMP reaction can be conducted under isothermal condition [12]. It is low cost, requires no electricity, provides rapid results and can be performed by minimally trained health workers [13]. Studies have found that LAMP has a comparable sensitivity and specificity to PCR, and is superior to microscopy and RDTs [14]. The method can detect parasitaemia as few as 1 parasite/ μ l of blood or lower, below the detection limit of microscopy or RDTs [12,15]. This is particularly important in pregnant women, where sequestration of parasites in the placenta is associated with low level parasitemia in peripheral blood [3]. This would lead to cases of chronic malaria going undetected. Although microscopy is considered as a gold-standard method, several nucleic acid amplification techniques have been evaluated for the diagnosis of malaria in the general population and also in pregnant women. Rantala and colleagues (2010) compared a real-time PCR assay and conventional microscopy for the detection of *P. falciparum* in Malawi. Of the 475 women, *P. falciparum* was detected in 11 (2.3%) by microscopy and in 51 (10.7%) patients by real-time PCR, thus questioning the accuracy of microscopy in this population.

Our group conducted a cross-sectional study in North Gondar, Ethiopia in 2014 to evaluate the use of LAMP in combination of a non-instrumented nucleic acid amplification (NINA) heater for the diagnosis of malaria. Using nested PCR as reference, the sensitivity and specificity of the primary NINA-LAMP assay were 96.8% (83.2% - 99.5%) and 84.3% (71.4% - 92.9%), respectively for detection of *Plasmodium* genus. Microscopy demonstrated sensitivity and specificity of 93.6% (78.5% - 99.0%) and 98.0% (89.5% - 99.7%), respectively for the detection of Plasmodium parasites. Post-hoc repeat NINA-LAMP analysis showed improvement in diagnostic accuracy, which was comparable to nested PCR performance and superior to microscopy for detection at both the *Plasmodium* genus level and *P. falciparum* parasites[10]. Recently, our group also showed the usefulness of LAMP for the diagnosis of malaria in pregnant women with 100% sensitivity achieved in a cohort of 87 women diagnosed with malaria [9]. What remains to be demonstrated is that gains in sensitivity with LAMP translate to improved outcomes for mother and child. Malaria contributes very significantly to maternal anemia and fetal mortality [16]. Pregnant women are three times more likely to suffer from severe malaria compared to the non-pregnant control population. Pregnant women infected with malaria usually have more severe symptoms and outcomes, with higher rates of miscarriage, intrauterine demise, premature delivery, low-birthweight neonates, and neonatal death. Chronic non-fatal infections also lead to complications with

the main problems being maternal anemia, intra-uterine growth retardation [2] and low birth weight.

In sub-Saharan Africa, anemia reportedly accounts for about 20% of all maternal deaths [17]. It is estimated that in areas where malaria is endemic, around 19% of infant low birth weights are due to malaria and 6% of infant deaths are due to low birth weights caused by malaria [18]. Low birth weight is thought to be the single biggest risk factor for neonatal and infant mortality [16]. These complications are so commonplace and severe that most countries in sub-Saharan offer intermittent presumptive therapy (IPT) to pregnant women, but resistance rates to the drug used (sulfadoxine-pyrimethamine) are very high and compliance with the full 3 doses during pregnancy poor. Other interventions include insecticide treated nets (ITN) and effective educational outreach programs [19].

Low-level parasitemia also have a role in disease in the non-pregnant population. Recent studies have pushed for asymptomatic malaria to be termed chronic malaria instead, with a view that even low level parasitemia can lead to severe health and economic consequences[20]. Additionally, as malaria incidence continues to fall, asymptomatic carriers with a low level parasitemia become more important in reducing transmission. They are thought to contribute to the malaria reservoir which leads to ongoing transmission by mosquitoes. Identifying and treating this group will be essential if the fight to eradicate malaria is to succeed.

An accurate parasite-based diagnosis of malaria is essential for proper treatment of the individual patient. Reliably excluding the diagnosis is equally valuable, because this will guide the clinician to consider an alternative diagnosis, which can be lifesaving [21]. A correct diagnosis is also important for public health, because avoidance of inappropriate antimalarial treatment will reduce costs and helps prevent the spread of drug resistance.

2. SIGNIFICANCE OF THE STUDY

Malaria in pregnancy often results in high degree of morbidity and mortality of the pregnant mother and the fetus. Early and accurate diagnosis of subclinical infections will be critical to malaria elimination and specifically the goals of the World Health Organization to reduce the burden of disease by 90% before 2030. This goal can only be achieved using highly sensitive methods such as LAMP that are capable of detecting subclinical infections with very low parasitemia. Currently both Giemsa stained blood film microscopy and RDT are the only laboratory methods that are used to diagnose malaria both in pregnant mothers and the general population. This leaves a big gap in the detection of low-level infections and asymptomatic malaria due to the documented lack of sensitivity of the aforementioned methods. This, in turn, predisposes pregnant mothers to malaria-related complications that endangers the life of the mother and the fetus. In this study, we propose that the use of a highly sensitive LAMP technique will enable us to detect more asymptomatic *Plasmodium* infections in pregnant women. This consequently results in early treatment of the pregnant mothers and may avert maternal and fetal morbidity and mortality. This study is of particular importance in Ethiopia where IPT is not used for pregnant women and therefore accurate screening is paramount.

3. PILOT DATA

At the time of writing, the phase 1 proof of concept retrospective study is complete. Phase 1 data are shown in Table 1 and 2 demonstrating the superior performance of LAMP technology compared to traditional methods. In particular, LAMP was able to detect up to 30% more malaria infected women than traditional methods using passive case detection (i.e., only symptomatic women).

	Frequency*	
Variable	Positive	Negative
	N (%)	N (%)
Age 18-24	3 (13.0)	20 (87.0)
25-30	5 (10.9)	41 (89.1)
31-35	1 (7.1)	13 (92.9)
36+	1 (25.0)	3 (75.0)
Previous malaria history		
Yes	5 (11.4)	39 (88.6)
No	5 (11.6)	38 (88.4)
Trimester		
First	2 (13.3)	13 (86.7)
Second	5 (13.9)	31 (86.1)
Third	3 (8.3)	33 (91.7)
Gravidity		
Primigravidae	2 (9.1)	20 (90.9)
Multigravidae	8 (12.3)	57 (87.7)

Table 1: Demographic and clinical features of pregnant women enrolled in the phase 1 retrospective evaluation of LAMP (commercial) versus traditional malaria diagnostic methods.

* As determined by PCR.

Table 2: Performance of LAMP compared to microscopy and RDT in symptomatic pregnant women (N=87, Gondar, NW Ethiopia), phase 1 retrospective study.

Method	Sensitivity % (95%CI)	Specificity % (95%CI)
Microscopy	90 (66.3-100)	98.7 (96.5-100)
RDT	70 (33.8–100)	97.4 (92.9–100)
LAMP	100 (100)	93.5 (86.5-100)

In phase 2 proof of concept, we compared ELUCIDx and a commercial LAMP assay to traditional diagnosis (RDT and microscopy) in both asymptomatic and symptomatic pregnant women in a

prospective fashion at three antenatal clinics. Our most complete data to date is from Jawi Health Centre in Amhara Region during the 2018 peak transmission season. In this study population, 28 of 34 pregnant women (mean age 24.2 years) who presented to the antenatal clinic were asymptomatic, 26 of 34 were in the first trimester, and 13 of 34 were primigravida. Malaria positivity amongst asymptomatic women was 3/34 (8.8%) by microscopy, 1/34 (2.9%) by RDT, 12/34 (35.3%) by commercial LAMP, and 12/34 (35.3%) by ELUCIDx, and 11/34 (32.3%) by qPCR. The sensitivity of microscopy in pregnant women in this study population was 25.0% (95% CI 5.49 - 57.19%), RDT 8.33% (0.21 - 38.48)), commercial LAMP 81.82% (48.22 - 97.72), ELUCIDx 100.00% (73.54 -100.00) and qPCR 91.67% (61.52 - 99.79) using a consensus gold standard. These data suggest that ultrasensitive diagnostics like LAMP are able to detect malaria far more frequently than traditional diagnostic methods when coupled to active case detection of symptomatic and asymptomatic pregnant women. The marked decrease in sensitivity for microscopy and RDT in phase 2 as compared to phase 1 is directly linked to the low level of infection found in asymptomatic pregnant women. We predict that greater detection of malaria in pregnancy with LAMP-based active case detection will lead to better critical outcomes such as LBW in pregnancy in the full-scale LAMPREG trial.

Table 3: Performance of LAMP compared to microscopy and rapid diagnostic tests (RDT) in asymptomatic and symptomatic pregnant women (N=34, Jawi, Amhara Region), phase 2 proof of concept prospective study with active case detection.

Method	Sensitivity % (95%CI)	Specificity % (95%CI)
Microscopy	25.00 (5.49 - 57.19)	100.00(84.56 - 100.00)
RDT	8.33 (0.21 - 38.48)	100.00(84.56 - 100.00)
Meridian LAMP (competitor)	81.82 (48.22 - 97.72)	86.96 (66.41 - 97.22)
ELUCIDx LAMP	100.00(73.54 -100.00)	100.00 (84.56 - 100.00)
qPCR	91.67 (61.52 - 99.79)	100.00 (84.56 - 100.00)

In additional preliminary data from Gojeb, Southwest Ethiopia, our study team has shown that treating pregnant women positive by LAMP has benefits in terms of fetal hemoglobin and birth weight, with the former reaching statistical significance (n=200, p<0.05). This is important data which requires confirmation in a full-scale trial across several epidemiological settings in Ethiopia.

Outcome			p Value
measure	LAMP Arm Mean (n=150)	SOC Arm Mean (n=50)	(t test)
Birth Weight (g)	3059	2965	0.1478
Mat Hgb 1 st			
visit (g/dL)	12.11	12.01	0.4981
Mat Hgb 2 nd			
visit (g/dL)	11.68	11.63	0.7211
Mat Hgb 3 rd			
visit (g/dL)	11.33	11.24	0.4606
Mat Hgb at			
birth (g/dL)	11.51	11.55	0.771
Fet Hgb at birth			
(g/dL)	13.1	12.84	0.04286

Table 4: Outcome measures in pregnant women (n=200) randomized to LAMP versus standard of care microscopy/RDT in Gojeb, Ethiopia.

4. OBJECTIVES

4.1. General objective

To assess the impact of LAMP in the diagnosis of malaria in pregnancy and its potential role in reducing mortality and morbidity attributable to malaria. We hypothesize that the additional sensitivity of LAMP coupled with active case detection in detecting malaria in pregnancy will result in additional cases being identified and treated.

4.2. Specific objectives

- 1. To evaluate the impact of LAMP versus microscopy/RDT for the detection of malaria in pregnant mothers in terms maternal and infant morbidity and mortality.
- 2. To evaluate the impact of enhanced case detection of malaria in pregnancy by screening asymptomatic mothers at each antenatal visit until delivery.
- 3. To determine the impact of treating LAMP-positive asymptomatic and symptomatic pregnant women as compared to standard of care. Treatment is per national guidelines.

5. MATERIALS AND METHODS

5.1. Study area

The study will be conducted at sites across several sites in Ethiopia to obtain sufficient enrolment and spanning different transmission settings based on epidemiological data provided by the Federal Ministry of Health. The study sites selected are Chisabay, Hamusit and Andasa Health centers; northwest Ethiopia, from southwest Ethiopia; Bonga area (Uffa Health Center and Bonga (GebreTsadik Shawo) General Hospital) and one site from Gambela (Lare Health center); in which some are sites where preliminary data were gathered. In Ethiopia, malaria is characterized by its seasonality where the peak transmission season is from October to December with a second peak in June. *P. falciparum* and *P. vivax* are the predominant species in the area [22]. Residents often live in non-substantive accommodation and despite a scale up in preventative measures in 2005 including ITN distribution, they are at risk of malaria.

5.2. Study design and period

The study is prospective diagnostic study of malaria in pregnant women. The goal is to determine whether: (i) LAMP provides a clinically measurable benefit compared to current first line diagnostic test of Giemsa-stained microscopy and whether (ii) enhanced case detection of asymptomatic mothers with LAMP has added value in terms of outcomes. We hypothesize that addition of LAMP to one arm will be of greater benefit than microscopy alone due to additional LAMP sensitivity. We further hypothesize that enhanced case detection by screening asymptomatic mothers at each antenatal visit will be of additional value in treating malaria. Both oniversity of cargary conjoint nearth research ethics board (CIRED) number. RED17 = 1355 ClinicalTrials.gov Identifier: NCT03754322

symptomatic and asymptomatic first and second trimester mothers will be included in the study and individually randomized to one of two arms: standard of care or enhanced cased detection arms using LAMP for malaria. Mothers will be enrolled during a twelve-months period from October 2020 to October 2021 and then followed until 28 days after delivery. Given the rate of pregnant mothers at the locations, we anticipate that the required minimum of 2583 mothers will be enrolled in the study during the study period. In the first standard of care arm, venous blood sample will be collected from each study participant and the presence of *Plasmodium* infection will be diagnosed by microscopy in symptomatic patients. Pregnant women who test positive for malaria will be referred and treated for malaria with quinine or ACTs as per national guidelines. In the second (test) arm, mothers whether symptomatic or asymptomatic will be tested by a commercially available CE-approved LAMP malaria test (Meridien Biosciences, Illumigene Malaria M kit, Cincinatti, USA) and Human Diagnostics LoopAMP (Wiesbaden, Germany) at each clinic visit in addition to RDT/microscopy. The commercial LAMP tests can distinguish P. falciparum and P. vivax and treatment will be given according to national guidelines. The purpose of doing all tests in the intervention arm is to determine how many additional cases LAMP identified. The primary outcome is the proportion of deliveries with low birth weight, with secondary outcomes of: (i) absolute birth weight; (ii) maternal hemoglobin; (ii) neonatal hemoglobin at birth (Standard Hgb testing from peripheral blood or finger prick); (iv) neonatal mortality; (v) stillbirth; and (vi) prematurity in each of the two arms. Additionally, signs of current or past *Plasmodium* sequestration in the placenta will be evaluated.

[figure not shown]

Figure 1: Flowchart summarizing randomized trial

There will be a total of at least five antenatal visits (mandatory). Emergencies (medical consultation outside the planned visit) will be recorded for each included woman. Visit 1 and 2 may be combined for mothers who present in the second trimester. The following table summarizes the procedures to be conducted at each visit.

Visit #	Time frame	Aim	Action for the study
1	Visit at health care center	Inclusion	Enrolment and randomisation
2	26 weeks gestation	Follow up	Malaria testing as per inclusion arm (2mL venous blood on EDTA) +ANC regular care Maternal Hgb
3	32 weeks gestation	Follow up	Malaria testing as per inclusion arm (2mL venous blood on EDTA) +ANC regular care Maternal Hgb
4	36-38 weeks gestation	Follow up	Malaria testing as per inclusion arm (2mL venous blood on EDTA) +ANC regular care Maternal Hgb
5	Delivery	Delivery visit	Foetal Hb Maternal Hb Malaria testing Birth weight + size Weeks of pregnancy - preterm? Placenta blood Death
6	28 days after birth	Néonatal assessment visit	Newborn weight/ hemoglobin/ death/ other

Table 5: Actions to be taken at each visit to the health center by a pregnant mother

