In case of adverse events during the study, women will be referred to a hospital and the event will be notified to study investigator. Contact of study investigators are available to women through inclusion forms. Women having any concerns regarding study procedure will be welcome to ask precisions to medical officers at any time during the LAMPREG trial. Study investigators will monitor adverse events from each study site on a monthly basis and take appropriate measures if needed. Since the LAMPREG trial is integrated with regular ANC visit, women participation in the study will not be noticeable by other community members, ensuring confidentiality.

The LAMPREG trial intervention arm consists of asymptomatic women screening for malaria during each ANC visit with highly sensitive techniques. The major added risks are due to the blood sampling. All material used will be single-used sterile needles. Medical staff will be vigilant on communication and will be explaining the steps of the study to the participants. Women tested positive for malaria will be administered treatment according to national guidelines pending on the gestational age. Before treatment administration, women will be explained the results of the LAMP test and the potential benefits of treatment.

At delivery, women are particularly vulnerable. The LAMPREG trial staff will respect women privacy during delivery. LAMPREG data collection and sampling will not affect the care given to the women and the newborn during delivery, and absolute priority will be given to the mother and child health and safety. For placenta blood collection, study staff will remind women about the procedure before sampling, and women will be allowed to withdraw consent.

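### Table 5 omits the entry malaria test that the text requires in the LAMP arm, and the merge of Visits 1 and 2 has no week limit, so early second-trimester entrants can lose the 26-week screen

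*Protocol*

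**What the plan says.** The text is consistent on how often the LAMP arm is screened. The Protocol Summary has these women receive the "LAMP malaria test and microscopy/RDT for malaria at each clinic visit and treated if positive by any test". Section 5.2 repeats that LAMP is done "at each clinic visit in addition to RDT/microscopy". Section 4.2 makes it an objective to evaluate "screening asymptomatic mothers at each antenatal visit until delivery", and section 5.12 describes the intervention arm as "asymptomatic women screening for malaria during each ANC visit with highly sensitive techniques". In the standard-of-care arm, section 5.2 provides for microscopy in symptomatic women.

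Table 5 in section 5.2 sets the schedule. The action at Visit 1 is "Enrolment and randomisation" and nothing else. The entry "Malaria testing as per inclusion arm (2mL venous blood on EDTA" first appears at Visit 2 (26 weeks). It recurs at Visit 3 ("32 weeks gestation") and Visit 4 (36-38 weeks). Visit 5 is delivery, which also includes a malaria test, and Visit 6 is 28 days after birth.

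The paragraph above the table makes at least five antenatal visits mandatory and adds: "Visit 1 and 2 may be combined for mothers who present in the second trimester". The only condition is the trimester. The protocol does not say in which week the second trimester starts. Entry is allowed up to 28 weeks (section 5.4), or below 27 weeks in the SAP (Section 5, item 2).

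**The concern.** Repeated screening of asymptomatic women is what separates the two arms, so a scheduled screen that drops out removes part of the intervention. There are two ways this can happen.

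First, the table and the text disagree about entry. Sites usually work from the visit table, and this one shows no malaria test at Visit 1.

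Second, the merge sentence is wider than its evident purpose. A woman who enters at or after 26 weeks needs Visits 1 and 2 combined. A woman who enters months earlier does not, yet the sentence allows it. Her combined visit would carry Visit 2's test at entry, and nothing further would be scheduled until 32 weeks. A new asymptomatic infection in that interval would have no planned screen. She would also have no 26-week hemoglobin, although the SAP (Section 6, item 1) reports maternal anemia at each antenatal visit.

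**Working it through.** The plan states no maximum or intended interval between tests, so there is no figure of its own to reproduce. The check is subtraction on the Table 5 weeks.

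**Inputs.** Visit 2 at 26 weeks, Visit 3 at 32, Visit 4 at 36-38 (Table 5). Upper entry limit 28 weeks (section 5.4) or below 27 (SAP). Assumption: the second trimester starts at 14 weeks; 13 is shown as an alternative. The calculation is for a LAMP-arm woman. In the standard-of-care arm a test at the merged visit would depend on symptoms.

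**Step 1: table against text, no merge.** Testing at each clinic visit includes Visit 1. The table has no test there. Under the table alone, a 14-week entrant has her first scheduled screen at 26 weeks, 26 - 14 = 12 weeks after entry.

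**Step 2: effect of a merge, with Visit 1 tested as the text requires.** For entry week g:
- merged: gap from entry test to Visit 3 = 32 - g
- unmerged: longest gap = max(26 - g, 32 - 26)

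| Entry week | Merged gap | Longest unmerged gap | Added by merge |
|---|---|---|---|
| 14 | 18 | 12 | 6 |
| 16 | 16 | 10 | 6 |
| 18 | 14 | 8 | 6 |
| 20 | 12 | 6 | 6 |
| 22 | 10 | 6 | 4 |
| 24 | 8 | 6 | 2 |
| 25 | 7 | 6 | 1 |
| 26 | 6 | 6 | 0 |

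With a trimester start of 13 weeks the top row would be 19 against 13, again 6 weeks added.

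**Step 3: scheduled tests before delivery.**
- Visit 1 tested: unmerged = entry, 26, 32, 36-38 = 4; merged = entry, 32, 36-38 = 3.
- Visit 1 not tested (Table 5 taken literally): unmerged = 26, 32, 36-38 = 3; merged = entry, 32, 36-38 = 3.

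Under the literal table, merging at 14 weeks costs no test and brings the first one forward by 12 weeks. The two defects therefore interact: restricting the merge without adding the Visit 1 test could delay some women's first screen.

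**Step 4: how wide the rule is.** It covers entry from 14 to 28 weeks, a span of 14 weeks. Of these, 26 - 14 = 12 lie before Visit 2 falls due. Only 28 - 26 = 2 need a merge (under 1 with the SAP limit). These are spans of gestational age, not shares of women.

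**Step 5: visit count.** Table 5 has five visits through delivery. An early merge leaves four: entry, 32 weeks, 36-38 weeks and delivery. Five is reached only if the 28-day visit is counted.

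**Step 6: comparison with early entry.** A woman who enters at 8 weeks, is tested then and is not merged waits 26 - 8 = 18 weeks for Visit 2.

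**The case against.** The strongest reply is that the merge rule is permissive and sits beside a table that fixes Visit 2 at 26 weeks. Sensible staff would merge only when a woman presents near that week. Nothing in the protocol says that a 14-week attendance satisfies a 26-week visit. The five-visit minimum in the same paragraph also works against early merging, unless it was set at five out of six precisely to allow for a merge. Extra antenatal attendances would trigger LAMP under the each-visit wording. All of this is fair. It makes 18 weeks a ceiling on the scheduled gap, not an expected unscreened period. It does not supply the missing week, and it does not repair the Visit 1 row.

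A second reply is that the basic schedule already tolerates 18 weeks for an 8-week entrant, and no document sets a maximum interval. That also stands. The point against the merge is that it drops a screen already scheduled for that woman, not that 18 weeks breaches a stated limit.

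Third, the SAP relies on Table 5 of protocol v1.5 (Section 3, item 7). The supplied protocol is v1.1, so the schedule may already have changed.

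A reader might go further and infer that the comparison is biased, that women will go 18 weeks unscreened, or that the low-birth-weight result is compromised. The documents support none of these. The merge is available in both arms and does not affect allocation. Gestational age at trial entry is not given; in the Jawi pilot (section 3), 26 of 34 women were in the first trimester, so those eligible to merge may be a minority. Nothing in the plan allows an effect on birth weight to be calculated. Nor can one infer that the LAMP arm is meant to go untested at entry, since the text says the opposite.

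**Conclusion.** The point holds as a minor design defect with two linked parts. In protocol v1.1, Table 5 contradicts the text by omitting the LAMP-arm test at Visit 1. The merge rule, limited only by trimester, lets an early second-trimester entrant lose the 26-week screen.

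If Visit 1 is tested, the loss is one of four scheduled pre-delivery tests. The longest scheduled gap rises by up to 6 weeks, from 12 to 18 for entry at 14 weeks. By entry at 26 weeks the added gap is nil. The early merge also sits badly with the five-visit minimum unless the 28-day visit counts.

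These figures rest on an assumed 14-week trimester start, on sites choosing to merge early, and on v1.5 carrying the same text. The consequence is weaker and less uniform delivery of the screening intervention in an unknown number of women.

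**What to change.** Check Table 5 and the merge sentence in protocol v1.5 first. If they are unchanged, make these edits together:

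- (a) Add arm-specific malaria testing to the Visit 1 row of Table 5, in the same terms as the Visit 2 row.
- (b) Limit the merge to women who enter close to or after 26 weeks. Suggested wording: Visits 1 and 2 may be combined for women who enter at 24 weeks or later; women who enter earlier attend Visit 2 at 26 weeks. The clinical team should set the floor. A floor of 24, 25 or 26 weeks limits a merged woman's gap to Visit 3 to 8, 7 or 6 weeks (32 minus the floor).
- (c) State how a merged woman meets the five-visit minimum, and whether she counts as adherent under SAP Section 4, item 2, which requires all antenatal visits to be completed.

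Edit (b) should not be made without (a).

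The cost is one table row and two or three sentences. Some second-trimester entrants attend a 26-week visit that is already in the schedule, with one more LAMP test each in the intervention arm. Where sites would otherwise follow the table, (a) adds an entry test for unmerged LAMP-arm women that the text already requires. No new procedure is introduced. The long wait of first-trimester entrants is not changed by these edits.
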